#### 5.3. Inclusion criteria

- 1. Histologically confirmed metastatic urothelial carcinoma not amenable to curative treatment with surgery or radiotherapy. Mixed histology is permitted if predominantly TCC.
- 2. Received a minimum of 3 cycles and maximum of 6 cycles of open label atezolizumab treatment\* (either first, second or third line¥) with an overall best response of stable disease according to local investigator assessment.
- 3. At least one extra-cranial metastatic site suitable for radiotherapy (see section 9.1).
- 4. At least one RECIST v1.1 measurable lesion distant to the planned site of radiotherapy.
- 5. No radiotherapy within four weeks prior to starting pre-study atezolizumab or during atezolizumab treatment.
- 6. Satisfactory haematological and biochemical profile (Hb >90 g/L, Plt>100 x  $10^9$ /L, WBC > 3.0 x  $10^9$ /L, creatinine < 1.5 ULN, AST or ALT <3X ULN, bilirubin <1.5x ULN).
- 7. ECOG PS 0-1.
- 8. Age ≥18 years.
- 9. Written informed consent.
- \* In accordance with therapeutic indications as stated in the current summary of product characteristics
- Neoadjuvant treatment received more than a year prior to trial entry will not be considered a line of treatment.

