#### **Footnotes**

- 1. Blood samples to be taken at RECIST v1.1 progression (if this did not occur at 9 weeks).
- 2. Within 28 days before randomisation.
- 3. QoL to be assessed at 6 months for all sub-study patients and 12 months for all sub-study patients who are still being treated with atezolizumab.
- 4. FFPE tumour tissue samples will be requested retrospectively and should not be sent without the prior notice of ICR- CTSU.

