#### 9.2.4. Duration of atezolizumab treatment

Participants will receive treatment until loss of clinical benefit or unmanageable toxicity up to a maximum of two years after starting RE-ARM allocated atezolizumab.

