#### Secondary endpoints

Objective response rate according to iRECIST and clinical benefit according to RECIST v1.1 will be compared between trial arms as per the primary endpoint. Best response will be tabulated according to trial arm.

Duration of response, time to progression, progression free survival and overall survival will be presented according to trial arm using Kaplan-Meier survival plots and analysed using log-rank tests and Cox proportional hazards models. Rates of progression free and overall survival will be estimated at 12 and 24 months.

Treatment-related toxicity will be presented according to grade and trial arm.

Quality of life data will be analysed using standard algorithms to derive scores and handle missing data according to the questionnaire's scoring manual. The primary outcome measure for patient reported quality of life will be overall quality of life measured by the EORTC QLQ-C30 global health/quality of life subscale score, which will be treated as a continuous variable. Subscale scores will be compared between treatment groups at individual time points, as well as the change from baseline to Week 9 and 6 months, using ANCOVA adjusting for baseline scores. Additional analyses of EORTC QLQ-C30 subscales will dichotomise change in subscale scores from baseline to each follow-up timepoint according to whether or not patients have experienced a deterioration of >10 points, and compared between groups using chi-squared tests or Fisher's exact test, as appropriate. Analyses to account for the longitudinal nature of the data (generalised estimating equations) may also be used. Secondary QoL outcomes of interest include the EORTC QLQ-C30 subcales for physical functioning, role functioning and fatigue, individual domains and utility scores from the EQ-5D-5L.

QoL sub-study patients who are still being treated with atezolizumab at 12 months will be asked to complete the questionnaire at this timepoint. QoL data for this subset of patients will be compared with their baseline QoL data taking into account relevant covariates including other treatments taken, to explore the impact of long term use of atezolizumab on QoL.

Exploratory analyses will be conducted to investigate whether response varies according to site of target lesion. Details will be specified in the Statistical Analysis Plan.

Analyses of efficacy outcomes will be by intention-to-treat; safety analyses will be in the per protocol population.

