### **A5.7 Statistical considerations**

Standard algorithms will be used to derive scores and handle missing data according to the questionnaire's scoring manual. Specifically, if at least half of the items from the scale have been answered, we will assume the missing items have values equal to the average of those items which are present for that respondent. The primary outcome measure will be overall quality of life, measured by the EORTC QLC-C30 qlobal health/QoL subscale score. Secondary QoL outcomes of interest include the EORTC QLQ-C30 subcales for physical functioning, role functioning and fatigue, individual domains and utility scores from the EQ-5D-5L. Subscale scores will be compared between treatment groups at individual time points, as well as the change from baseline to Week 9 and 6 months adjusting for baseline scores. Additional analyses of EORTC QLQ-C30 subscales will dichotomise change in subscale scores from baseline to each follow-up timepoint according to whether or not patients have experienced a deterioration of >10 points. Analyses to account for the

longitudinal nature of the data (generalised estimating equations) may be used. At 12 months any patients who are continuing treatment with atezolizumab will be asked to complete the questionnaire. 12-month data will be compared with baseline data (taking into account relevant covariates including other treatments) to explore the impact of long term use of atezolizumab on QoL. To make some adjustment for multiple testing a significance level of 1% will be used for comparisons of quality of life endpoints. An analysis plan will be developed in consultation with the TMG.

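### The 12-month quality-of-life comparison in patients still on atezolizumab cannot show the impact of long-term atezolizumab and should be restated as descriptive

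*Protocol*

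**What the plan says.** Protocol 12.4 (Secondary endpoints) fixes who is measured at 12 months: "QoL sub-study patients who are still being treated with atezolizumab at 12 months will be asked to complete the questionnaire at this timepoint". It fixes the comparator: "QoL data for this subset of patients will be compared with their baseline QoL data", with adjustment for relevant covariates, including other treatments. It also fixes the purpose: "to explore the impact of long term use of atezolizumab on QoL". A5.7 repeats the plan ("12-month data will be compared with baseline data") with the same purpose. The restriction to patients still on drug is built into data collection in 8.3, 12.3.2, A5.5 and footnote 3 of the sub-study schedule (8.10.1).

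Four other places bear on the meaning of that comparison:

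- 5.3, criterion 2, on entry: "Received a minimum of 3 cycles and maximum of 6 cycles of open label atezolizumab treatment".
- 8.10.1, footnote 2, on the timing of the screening questionnaire: "Within 28 days before randomisation".
- 9.2.4, on how long patients stay on drug: "Participants will receive treatment until loss of clinical benefit or unmanageable toxicity", up to two years.
- 12.2: both randomised groups receive atezolizumab; only radiotherapy differs.

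A5.2 declares all quality-of-life testing exploratory because the trial is not powered for it.

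**The concern.** The stated purpose is a question about the effect of a drug. The planned data are one group's change over time, with no group off the drug, no value from before the drug, and membership decided after randomisation by how patients fared on it. If the 12-month scores are stable or better than at entry, the protocol's wording invites the reader to credit long-term atezolizumab, although selection alone could produce that picture.

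There is a second, smaller problem. 12.4 also compares subscale scores between arms at individual time points, and compares deterioration between arms at each follow-up timepoint. Read literally, both include 12 months. Such a test would compare arms within a set defined by staying on treatment, which radiotherapy could itself affect.

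**Working it through.** The protocol gives no figure for this analysis, so there is none to reproduce. The check is mainly a matter of setting the sections side by side.

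1. **Baseline.** Entry needs 3 to 6 earlier cycles (5.3). At three-weekly dosing that is 3 × 3 = 9 to 6 × 3 = 18 weeks of drug. The baseline questionnaire is completed at screening, up to 28 days before randomisation (8.10.1), so a few patients might complete it shortly before their third cycle, but still on drug. Early effects are already in the baseline. These could be losses or gains, so the direction of any resulting bias is unknown.
2. **Comparator.** All participants receive atezolizumab (12.2). Disease course, time and drug cannot be separated.
3. **Selection.** Treatment ends at loss of clinical benefit or unmanageable toxicity (9.2.4). Both are routes by which quality of life would be expected to worsen, so patients who took either route before 12 months are not asked at 12 months. Progression alone does not remove a patient: 8.5 allows treatment past RECIST v1.1 progression, and the footnote to 8.8 allows it past confirmed iRECIST progression if agreed with the Chief Investigator.
4. **Adjustment.** Covariates act only among patients who were measured and cannot stand in for those who were not.

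**Illustration of step 3. All inputs are assumptions; none comes from the documents.** Let f be the share still on treatment at 12 months, SD the standard deviation of change, and rho the correlation between change in quality of life and a latent normal propensity to stay on treatment. The mean change in those retained then differs from the mean in all patients by

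shift = rho × SD × phi(c) / f, where c is the normal quantile with upper tail f.

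With SD = 20 points:

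| f | phi(c)/f | rho = 0 | rho = 0.2 | rho = 0.4 | rho = 0.6 |
|---|---|---|---|---|---|
| 0.2 | 1.40 | 0 | 5.6 | 11.2 | 16.8 |
| 0.3 | 1.16 | 0 | 4.6 | 9.3 | 13.9 |
| 0.5 | 0.80 | 0 | 3.2 | 6.4 | 9.6 |

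Here rho is not the correlation with the observed yes/no status. If r is that correlation, the formula is r × SD × √((1 − f)/f); for r = 0.3 and f = 0.2 this gives 0.3 × 20 × 2 = 12 points. The table shows that the shift may be nil or substantial, and that the documents cannot tell us which.

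**Likely size of the set (also assumed).** If 20% to 40% of 102 patients are still treated and all join the sub-study, that is 102 × 0.2 ≈ 20 to 102 × 0.4 ≈ 41 patients, before questionnaire non-response.

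**The case against.** The strongest reply is that the protocol claims little. The wording is exploratory, A5.2 says all quality-of-life testing is exploratory, and the hypothesis there concerns 9 weeks and 6 months. The patient's own baseline removes selection on starting level. A trial that enrols patients already on the drug cannot have a pre-drug questionnaire, and change from entry to 12 months is a fair description of continued use. Covariates and methods can be settled in the analysis plan.

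Part of this stands. The analysis is secondary, commits to no conclusion, and is a legitimate description. But A5.2 gives lack of power as its reason, and neither more patients nor the 1% level in A5.7 would cure selection or supply a comparator. Pairing does not remove selection on the course of quality of life. The aim and the restriction on who is asked are fixed in the protocol itself, and no later plan can recover uncollected forms.

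Several stronger readings are tempting but unsupported:

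- A reader might infer that the analysis was designed to flatter the drug. The documents show a direction of selection, not an intent.
- A reader might infer that every progressing patient drops out. 8.5 and 8.8 say otherwise, and 9.2.8 lets treatment resume after many toxicities.
- A reader might infer that the trial discards its long-term randomised comparison. No 12-month comparison of arms was among its stated hypotheses, and the between-arm ANCOVA at week 9 and 6 months covers sub-study patients on or off drug.
- A reader might set the table against the threshold of more than 10 points in 12.4. That threshold classifies individual deterioration; it is not a benchmark for a mean.

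**Conclusion.** The point holds in a limited form. The 12-month comparison in 12.4 and A5.7 cannot show the impact of long-term atezolizumab on quality of life, because it lacks a pre-drug value and a drug-free comparator and is restricted by rule to patients with continued benefit and tolerability. This conclusion rests on the protocol's text alone.

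That selection would favour the drug rests on one further assumption: that patients who stop for loss of benefit or toxicity tend to have a worse quality-of-life course than those who continue. The size is not derivable; 0 to about 17 points is the span of the assumed inputs, not an estimate. The primary endpoint and the week 9 and 6-month randomised quality-of-life comparisons are untouched. The consequence is a possible misreading of a secondary exploratory result, which a small change of wording prevents.

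**What to change.** **Needed.**

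1. In 12.4 and A5.7, replace the aim about long-term use with a descriptive summary of quality-of-life change since trial entry among patients remaining on treatment, noting that the baseline was taken on drug.
2. Report by arm the number not assessed at 12 months and the reason: death, treatment stopped, or non-response.
3. State that the between-arm tests cover week 9 and 6 months only, because the 12-month set is conditioned on a post-randomisation outcome.

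This costs a few sentences and no new data collection beyond recording the reasons.

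**Optional.** Ask all surviving sub-study patients to complete the 12-month questionnaire whether or not they are on drug, and compare arms by the ANCOVA already planned, labelled exploratory. This changes 8.3, 12.3.2, 12.4, A5.5, A5.7 and footnote 3 of 8.10.1. Its costs are real. The three-monthly follow-up in 8.8 is for disease status and survival, whereas A5.5 places questionnaires at clinic visits, so delivery would have to be arranged, and more forms would be missing. Comparing arms among survivors is itself truncated by death, which must be reported. Section 1.1 cites 39% survival at 12 months with atezolizumab in the phase III trial against second-line chemotherapy; this trial's entrants differ, having stable disease after 3 to 6 cycles, but deaths before 12 months should be expected.

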#### 1.5. Study rationale

RE-ARM will explore whether the additional late responses as observed in IMvigor210 could be enhanced with radiotherapy in patients receiving atezolizumab for the treatment of metastatic urothelial carcinoma.

IRAS 280335 / CCR5167

PD1/PD-L1 treatment has proven benefit for a subset of patients with metastatic urothelial carcinoma. As the study tests a drug-radiation combination therapy, a randomised design was selected to enable quantification of the impact of radiotherapy on response, given that a late response is observed in a subset of patients receiving atezolizumab in the absence of additional intervention. As tumour shrinkage is hypothesised (the abscopal effect), response was deemed a preferable primary endpoint over progression-free survival. If this study demonstrates that radiotherapy treatment increases atypical responses in patients on PD-L1 therapy with minimal impact on toxicity, this could substantially expand the number of patients who benefit from immunotherapy treatment. The trial has a two stage design to allow early termination if sufficient activity is not observed in the experimental group.

Translational work within the study may offer insights to the dynamic process of PD-L1 expression and immune activation that may have implications for tumours that are currently unresponsive to immune therapy across cancer types.

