# 8.8. Discontinuation from treatment and post-treatment follow up\*

Participants may discontinue from trial treatment at any time at their own request, or they may be discontinued at the discretion of the Principal Investigator. Reasons for discontinuation may include:

- Disease progression or recurrence
- Loss of clinical benefit
- Unmanageable toxicity
- Pregnancy

Participants who discontinue treatment should continue to have scans at protocol determined intervals until RECIST v1.1. progression or commencement of further systemic treatment. Participants should be followed up:

- For disease status and survival every three months up to two years after study entry and every six months thereafter.
- Patients should be monitored for immune related toxicity for 90 days post treatment completion or until initiation of further systemic treatment, if sooner.

\*Patients with confirmed iRECIST progression (iCPD) would be expected to discontinue study atezolizumab. If it is considered in the patient's best interest to continue treatment this should be discussed with the RE-ARM Chief Investigator (via [contact]) and, once agreed, the patient should continue to be followed up as per iUPD until treatment discontinuation (see Appendix A4).

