# 9.1.3. Radiotherapy treatment technique

The radiotherapy dose will be 20Gy in 5 fractions to be delivered over 1 week.

Treatment can start on any day of the week.

The treatment technique will be as per normal clinical practice with the aim of delivering treatment with minimal toxicity. Conformal or IMRT/VMAT delivery will be preferred but less complex fields will be accepted e.g. single fields to spinal vertebrae.

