Further details of analysis methods including definitions of analysis populations will be specified in a Statistical Analysis Plan in accordance with ICR-CTSU Standard Operating Procedures.

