### A2. iRECIST

### **A2.1 Definitions**

• Evaluable for adverse events.

All patients will be evaluable for adverse event evaluation from the time of their first treatment.

• Evaluable for response.

All patients who have received at least one cycle of therapy and have their disease reevaluated will be considered evaluable for response (exceptions will be those who exhibit objective disease progression prior to the end of cycle 1 who will also be considered evaluable). Patients on therapy for at least this period and who meet the other listed criteria will have their response classified according to the definitions set out below.

Response and progression will be evaluated in this study using the revised international criteria (1.1) proposed by the RECIST (Response Evaluation Criteria in Solid Tumours) committee as well as the modified iRECIST guidelines. Investigators should note the different requirements for confirmatory scans as well as follow up for the two criteria.

See appendix A4 for criteria for continuing treatment past RECIST 1.1 disease progression.

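### Section 12.4 assigns safety to the per protocol population, a set that by its usual meaning can drop treated patients and could understate the added harm of radiotherapy

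*Protocol*

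**What the plan says.** The closing lines on secondary endpoints in Section 12.4 of the protocol set two populations against each other. For efficacy: "Analyses of efficacy outcomes will be by intention-to-treat". For safety: "safety analyses will be in the per protocol population". The same section then defers the detail: "Further details of analysis methods including definitions of analysis populations will be specified in a Statistical Analysis Plan". The protocol therefore names the safety set but does not say who belongs to it, and nowhere provides for a safety analysis in all treated patients.

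On the output, Section 12.4 says: "Treatment-related toxicity will be presented according to grade and trial arm".

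Appendix A2.1 takes a different line on who counts for adverse events: "All patients will be evaluable for adverse event evaluation from the time of their first treatment". Sections 11.2 and 11.3 likewise collect adverse events, serious adverse events and events of special interest from the start of study treatment, with no condition on adherence.

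**The concern.** The standard safety set is everyone exposed, because harm is a consequence of exposure. A per protocol set selects on what happens after randomisation, and tolerance of treatment is part of what happens. Here the selection could also be uneven. Both arms receive atezolizumab, but only one has a radiotherapy schedule: "The radiotherapy dose will be 20Gy in 5 fractions to be delivered over 1 week". A control patient cannot miss a fraction.

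The comparison matters to the trial's conclusion. Section 1.5 makes the case for the combination depend on more responses "with minimal impact on toxicity", and toxicity is a listed secondary endpoint. Section 1.4 reports significant toxicity with a different and more intensive pelvic schedule given with another checkpoint inhibitor, and warns about dose-limiting toxicity. Added harm is therefore an open question in this trial, and the final safety tables are where a reader will look for the answer.

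**Working it through.** The protocol states no safety rate, so there is no figure to reproduce. The check has two parts.

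**1. The passages side by side**

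- Section 12.4 gives efficacy to the intention-to-treat set and safety to the per protocol set. The contrast suggests that the second set is narrower than all randomised patients.
- Appendix A2.1 and Sections 11.2 and 11.3 start from first treatment and set no adherence condition.
- Section 9.1.2 asks for radiotherapy to be finished before the second on-study cycle, and Section 9.1.3 fixes five fractions over a week. The only gap that Section 9.1.7 calls acceptable is up to 3 days for machine service or breakdown. A course interrupted or shortened for toxicity is not covered there, so a per protocol rule could treat it as a deviation.
- Section 8.8 lists "Unmanageable toxicity" among the reasons for stopping trial treatment. Stopping atezolizumab for toxicity is thus within the protocol and need not lead to exclusion.

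The plausible route to exclusion is therefore narrow: radiotherapy that was started and not completed as planned because of toxicity.

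**2. What such exclusions could do**

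Input from the protocol: n = 51 per arm (Section 5.1). Assumed inputs: x radiotherapy patients with grade 3 or higher toxicity, and m patients excluded, of whom k had the event.

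Reported rate = (x − k)/(n − m). This is below x/n only when k/m > x/n, that is, when the excluded patients have events more often than the arm as a whole.

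Take x = 10, so that the rate in all 51 is 10/51 = 19.6%, and suppose that every excluded patient had an event (k = m). For comparison, assume 5/51 = 9.8% on control with nobody excluded.

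| Excluded | Reported rate, radiotherapy arm | Difference from control |
|---|---|---|
| 0 | 10/51 = 19.6% | 9.8 points |
| 2 | 8/49 = 16.3% | 6.5 points |
| 3 | 7/48 = 14.6% | 4.8 points |
| 5 | 5/46 = 10.9% | 1.1 points |

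With x = 8 (15.7%) against the same control rate, the difference in all patients is 5.9 points. Excluding 4 affected patients gives 4/47 = 8.5%, and the difference becomes −1.3 points.

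The opposite case is also possible. If the 5 excluded patients had no event (k = 0, m = 5), for example because they were allocated radiotherapy but never received it, the reported rate is 10/46 = 21.7%, above 19.6%.

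**The case against.** The strongest reply is that the criticism supplies the definition it attacks. The protocol leaves the definitions of analysis populations to the SAP, which is not among the documents at hand. That plan could define the per protocol set as everyone who received at least one dose, in which case nothing is lost. This stands as far as it goes: no bias has been shown. It does not rescue the wording, because the protocol has already fixed the set by name. An SAP faithful to the name would restrict the safety set, and one that analysed all treated patients would have to use the name against its usual meaning.

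A reader might infer that patients who stop atezolizumab for toxicity would be left out. The documents do not support this. Sections 9.2.1 and 9.2.4 run treatment until loss of benefit or unmanageable toxicity, Section 9.2.8 lays down withholding and discontinuation for adverse reactions, and Section 9.2.9 covers long interruptions. Such patients have followed the protocol. The radiotherapy course is also short, so toxicity that appears after it ends cannot make it incomplete. Nothing in the protocol indicates how many patients would fail to complete it because of toxicity.

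Two further points carry some weight. Appendix A2.1 belongs to the iRECIST appendix and does not formally define the analysis sets of Section 12.4, so it is evidence of poor fit more than a flat contradiction. And harm is not hidden during the trial: event reporting and the data monitoring committee's toxicity review (Section 12.5) are not limited to a per protocol set. The exposure is confined to the final safety analysis.

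**Conclusion.** The point holds as a wrongly named analysis set. It is not merely a missing definition. The name permits the exclusion of treated patients, the opportunity for exclusion through radiotherapy deviations exists in one arm only, and the label does not fit the protocol's own rule on evaluability for adverse events.

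A reader might go further and conclude that the plan does bias toxicity downward, or that it halves the true rate. Neither follows. The true rate is unaffected; what could change is the reported rate. The fall from 19.6% to between 16.3% and 10.9% rests on assumed event counts and on the assumption that every excluded patient had an event. The size and the direction of any bias depend on the definition left to the SAP. What the arithmetic does show is that, with 51 patients per arm, a handful of selective exclusions is enough to alter the safety comparison.

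**What to change.** Replace the safety clause in Section 12.4 with: *Safety analyses will include all patients who received at least one dose of study atezolizumab or one fraction of trial radiotherapy, grouped by treatment received.* Since Section 9.1.8 permits palliative radiotherapy in both arms, make clear that the grouping refers to trial radiotherapy. Keep any per protocol safety summary as supplementary only, align Section 12.4 with Appendix A2.1, and carry the same definition into the SAP.

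The cost is one sentence. No new data are needed, because adverse events are already collected from the start of treatment. Sample size, significance level and power do not change: they rest on response, and efficacy stays on the intention-to-treat set.
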